Tertiary	To determine if the level of serum vitamin D at baseline correlate with colonisation of AMR bacteria in faecal isolates	Level of serum vitamin D and AMR colonisation within faecal sample	Baseline
Additional baseline measurements		Demographic information (to include age); clinical frailty score; use of proton pump inhibitors, laxatives and dose of Vitamin D	Baseline
Other		Record whether trial participant refused to give blood/saliva/stool sample	Over 12* months from care home resident record
		Ask care home staff what arm they think the trial participant is in	12 month CRF
		Record most common method of delivery of study product e.g. swallowed with water or sprinkled on food/drink	Over 12* months from MARS sheet
Qualitative sub-study	To understand how the trial was carried out within the care home context and to identify the mechanisms with affect implementation of trial activities	With trial participants; consultees; relatives or friends; care home managers; care home staff; and research nurses	At the end of data collection

\* The follow-up schedule will depend on the length of time that a participant has been in the study. Where possible, participants will have a baseline assessment, and three- and 12-month follow-ups. Due to time limitations, some participants may have a truncated follow-up and will receive either a baseline assessment and 3-month follow-up, or a baseline assessment, 3-month follow-up and a second follow-up between 6-10 months post-randomisation. Infection, antibiotic use, adverse events and study product use is also recorded at regular intervals by the RN from care home notes for 12 months post-randomisation or until 31/10/2018, whichever is sooner

All tissue samples donated by trial participants will be taken on the understanding that they may be used for future research projects in the UK. The samples will be stored and subsequently distributed to approved projects in accordance with the Human Tissue Act and ethical legislation. This statement will form part of the consent procedure.

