# **17 Statistical considerations**

## **17.1 Randomisation**

Participants will be individually randomised in a 1:1 ratio using minimisation. In order to achieve a balance of probiotic and placebo allocations within care homes, the care home from which a participant is recruited and gender of participant will be used as a minimisation variable. A random element, set at 80%, will be used in order to maintain the integrity of the minimisation process. The participants, treating clinicians, trial statistician and research nurses will remain unaware of the group to which participants are allocated during the trial. Pack IDs will be assigned probiotic / placebo allocations using randomly permuted blocks, and this list will be uploaded into the online system. This process will be carried out by a statistician independent of the trial team.

For more details, please consult the PRINCESS randomisation protocol.

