## **18 Analysis**

### **18.1 Main analysis**

The primary analysis will be by intention-to-treat, and will consist of a between-group comparison of the mean cumulative antibiotic administration days (CAAD) using Poisson regression. As the randomisation will be stratified by care home, the regression model will control for the care home a participant was recruited from. Negative binomial regression will be used in the presence of over-dispersed count data.

For secondary outcomes, depending on the type of data, a mixture of Poisson, linear, logistic and Cox models will be used to appropriately compare trial arms with respect to rates, means, proportions and time to events (see table below for more details).

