## **20.3 Risks and benefits**

Due to this being a randomised placebo controlled trial, half of the participants have no chance of benefit from the trial intervention. All participants (or their consultee), however, may value contributing to the advancement of medical knowledge and appreciate the increased assessments and monitoring. Probiotics are classed as a food supplement (and this has been confirmed by the MHRA for this trial) and there are very few side effects (mainly bloating and flatulence if these occur). Probiotics carry theoretical risks including infection beyond the gut, and transfer of antibiotic resistant genes. However, so far, there have been no reports of bacteraemia or fungaemia attributable to the probiotics in trials included in the systematic reviews and mild to moderate gastrointestinal side effects and rash are generally no more common than in patients on placebo probiotic.

For participants receiving the probiotic, reducing the possibility of developing an infection that may require treatment with an antibiotic, we believe, outweighs the risk of the potential side effects. If our hypothesis is correct and probiotics reduce antibiotic prescribing for CHR, this may also reduce the number of antibiotics prescribed for other CHR and subsequent AMR. For all participants, the high level of monitoring for common infectious diseases may result in better-targeted treatment and added vigilance in general.

Residents lacking capacity will be included in the trial as our previous PAAD observational study data demonstrated that those who lack capacity are frailer and receive antibiotics more often and for different indications than those with capacity and, therefore, may be more likely to benefit from interventions aimed at stimulating and supporting the immune system. Interventions should be evaluated in populations for whom the intervention is intended, especially when there are relevant material differences (e.g. in frailty and in immune function).

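### Allocation is minimised on care home and gender, but the primary CAAD model as written adjusts for care home only

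*Protocol*

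**What the plan says.** Section 17.1 of the protocol sets out the allocation: "Participants will be individually randomised in a 1:1 ratio using minimisation". It names two factors: "the care home from which a participant is recruited and gender of participant will be used as a minimisation variable". It adds that "A random element, set at 80%, will be used".

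Section 18.1 defines the primary analysis as a "between-group comparison of the mean cumulative antibiotic administration days (CAAD) using Poisson regression", with negative binomial regression if the counts are over-dispersed. It fixes one covariate and gives the reason for it: "As the randomisation will be stratified by care home", "the regression model will control for the care home a participant was recruited from".

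The CAAD row in section 18.2 names the Poisson model and the negative binomial alternative, with no covariate. Other rows of that table do name covariates, for example the baseline value in the EQ5D and stool-sample models.

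On frailty, section 5.1 lists among the baseline measurements "Demographic information (to include age); clinical frailty score". Section 20.3 says of residents in an earlier observational study that "those who lack capacity are frailer and receive antibiotics more often".

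**The concern.** Section 18.1 adjusts for care home because care home was used in the allocation. Section 17.1 shows that gender was used in the same way, so by the protocol's own reasoning the stated adjustment set is incomplete. Section 18.1 also calls the scheme stratified on one factor, whereas section 17.1 describes minimisation on two.

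The statistical issue is a familiar one. Balancing the arms on a prognostic factor removes that factor's contribution from the chance difference between arms. A model that omits the factor still counts its variation as residual noise. The reported standard error then becomes larger relative to the true spread of the estimate, and precision secured by the design is partly lost. There is also a matter of prespecification: the covariates of the primary model should follow from the design and should not be open to choice later.

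**Working it through.** **1. Allocation and model side by side.**

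| | Section 17.1 | Section 18.1 |
|---|---|---|
| Method | minimisation, 1:1, random element 80% | described as stratified |
| Factors | care home, gender | care home |
| Gender in the primary model | – | not named, nor in 18.2 |

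**2. The protocol's power figure.** Section 17.2 gives at least 82% power with 258 to 270 participants and about 250 days each, for 17.4 days per resident-year and a 10% reduction. With 129 per arm and a Poisson variance, the standard error of the log rate ratio is √[1/(129 × 250/365 × 17.4) + 1/(129 × 250/365 × 15.66)] = √(1/1537.4 + 1/1383.7) = 0.0371. Then ln(1/0.9)/0.0371 − 1.96 = 0.883, which gives 81.2% power. Using the stated 15.6 days gives 83.7%. The stated figure is reproduced to within 2 points. The formula has no covariate term, so adding gender does not change it.

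**3. Which model is likely to apply.** Section 3.3 gives 17.4 antibiotic days per year and section 4.2 gives 2.16 prescriptions per resident-year. 17.4/2.16 ≈ 8 days per course. Days arrive in blocks, so over-dispersion is to be expected and the negative binomial fallback is the relevant case.

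**4. Size under the negative binomial model.** Simulation with 264 participants (midpoint of 258 to 270), 20 homes, minimisation on home and gender with an 80% chance of the better-balancing arm, no treatment effect, and 800 trials per setting. Assumed, because the protocol does not give them: dispersion 1, 30% men, between-home SD 0.3 on the log scale, and the gender rate ratio.

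| Gender rate ratio | Mean SE, home only | Mean SE, home + gender | Excess |
|---|---|---|---|
| 1.0 | 0.1244 | 0.1241 | 0.1244/0.1241 − 1 = 0.2% |
| 1.5 | 0.1260 | 0.1243 | 0.1260/0.1243 − 1 = 1.4% |
| 2.0 | 0.1294 | 0.1249 | 0.1294/0.1249 − 1 = 3.6% |

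At a ratio of 2.0 the true spread of the estimate was 0.1349 with home only and 0.1320 with gender added. Standard error over true spread is therefore 0.1294/0.1349 = 0.96 without gender and 0.1249/0.1320 = 0.95 with it. Omitting gender moves the ratio upwards, the conservative direction, but it stays below 1. The rejection rate of the home-only model under no effect was 5.6% to 6.5% across the settings, so these runs give no sign of a test below its nominal level.

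**5. Other variance models**, same scheme and assumptions, 3000 trials per setting.
- Plain Poisson, ratio 2.0: SE 0.0311 without gender and 0.0312 with it, against a true spread of about 0.14. Gender makes no practical difference. The standard error is far too small because it ignores over-dispersion.
- Dispersion-scaled Poisson, a model the protocol does not name: at ratio 1.3, 0.1255 falls to 0.1239 (about 1%); at 2.0, 0.1338 falls to 0.1229 (about 8%). SE over true spread at 2.0 is 0.93 without gender and 0.87 with it.

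**6. Frailty.** In the dispersion-scaled model, with an assumed rate ratio of 1.5 per SD, adding frailty lowers the reported SE from 0.1386 to 0.1244 and the true spread from 0.1554 to 0.1445. The two fall together because allocation was not balanced on frailty.

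**The case against.** The strongest reply is that nothing of consequence follows from the mismatch. The protocol does not say whether gender predicts antibiotic days, and if it does not, omitting it costs nothing. Under plain Poisson regression the standard error does not respond to gender at all. Under the fallback the change is a few per cent even for a two-fold gender difference. A statistical analysis plan that is not shown may already include gender. All of this stands as a limit on the size of the point. It does not remove the inconsistency: section 18.1 is not silent on covariates but names one and gives a reason that covers two. An analysis plan that added gender would depart from that text.

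Three stronger readings may suggest themselves, and the documents support none of them:
- **That the standard errors are overstated and the test is conservative.** This needs gender to be prognostic, which is not shown. In simulations of the planned scheme, no home-only standard error exceeded the true spread of the estimate.
- **That leaving out frailty is an error of the same kind.** Frailty is not a minimisation factor, so omitting it gives up possible precision without making the standard error wrong. Section 20.3 compares residents with and without capacity; it links frailty to antibiotic use only through lack of capacity.
- **That every secondary model should carry both minimisation factors.** Section 7 expects about 20 care homes. Entering them all in logistic models for outcomes such as VRE or *C. difficile* risks sparse cells if events are few.

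**Conclusion.** The inconsistency between sections 17.1 and 18.1 is certain; its numerical effect is small and conditional. If gender predicts CAAD, the model as written loses some precision and shifts the standard error in the conservative direction, by about 1% to 4% under the negative binomial model for assumed gender rate ratios of 1.5 to 2.0, and by essentially nothing at 1.0. These sizes rest on the assumed dispersion, gender split, between-home variation and gender effect. The power stated in section 17.2 is not affected. This is a minor point of consistency and prespecification, worth correcting because the correction is nearly free.

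**What to change.** In section 18.1, replace the clause on stratification and care home with: *As allocation is minimised on care home and gender, the regression model will adjust for care home and gender.* This also corrects the description of the scheme. If gender is left out on purpose, give the reason there instead.

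The cost is one sentence and one extra parameter, on a variable already recorded for every participant because the minimisation needs it. In the simulations, including gender when it had no effect left the standard error practically unchanged (0.1244 against 0.1241).

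Optionally, the baseline clinical frailty score may be prespecified as a further covariate for precision. That is an improvement to consider, not a correction. Covariates for the secondary models should be decided outcome by outcome, with event numbers in mind.

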### **Adherence-adjusted analysis**

While our primary analyses will be conducted using the intention-to-treat principle (i.e. a comparison of groups as randomised regardless of what happens after randomisation), we will monitor adherence to study product throughout the trial. Using this data, we will perform adherence-adjusted analyses, deriving estimates of treatment efficacy that maintain a comparison of groups as randomised, using structural mean models (50). A definition of adherence to study product will be defined prior to the commencement of any statistical analysis.

### **Missing data assumptions and adjustments**

Given our proposed intensive monitoring schedule, missing data is likely to be minimal for participants who remain in the trial for the full duration. Where missing data is likely to occur, it will most likely be due to participant drop-out, with reasons for dropout falling into two broad categories, withdrawal from the trial and death.

Where responses are missing due to drop-out, these will be assumed to be missing at random given observed data, and appropriate modelling techniques will be used (e.g. likelihood-based methods or multiple imputation). Sensitivity analyses will be conducted using joint modelling approaches (e.g. selection and/or pattern mixture models) to explore departures from the missing at random assumption (51).

We will also explore stratifying deaths into two groups: death during an infection and death from any other cause. We will then investigate applying a missing at random-valid modelling approach to the deaths from any other cause and take a more extreme approach with those that died during an infection (e.g. assume that they would have remained on antibiotics for the remainder of the follow-up period).

Similarly, we will explore stratifying drop-out due to residents moving to another care facility into two groups: those who move for health-related reasons (e.g. from a residential home to a care home providing nursing care) and those who move for other reasons. A missing at random-valid modelling approach will be applied to the latter strata, with a more extreme approach taken for those dropping out due to moving from the care home for health-related reasons as this represents a decline in health, which may also be subject to unmeasured selection bias.

### **Analysis for mechanistic process**

Further statistical modelling will explore the causal mechanisms by which the probiotic may have an effect. Mediation analyses will explore the effect of exposure to probiotics on CAAD and cumulative number of infection days, and this is mediated through an effect on antimicrobial resistance. These analyses will be performed using G-computation (52, 53).

## 18.2 Description of outcomes and method of statistical analysis

Outcome	Main analysis	Sensitivity analyses*
Primary		
Cumulative antibiotic administration days (CAAD)	Poisson regression.	Negative binomial regression (if Poisson over-dispersed).
Secondary		
CAAD by infection (UTI, RTI, skin, GI, unexplained fever)	Poisson regression, with trial arm interacted with infection.	Negative binomial regression (if Poisson over-dispersed).
Incidence of infection	Poisson regression.	Negative binomial regression (if Poisson over-dispersed).
Site of infection	Poisson regression, with trial arm interacted with infection.	Negative binomial regression (if Poisson over-dispersed).
Mean duration of infection	A two-level Cox PH (frailty) model with infections nested within participants.	
Cumulative number of infection days	Poisson regression.	Negative binomial regression (if Poisson over-dispersed).
Antibiotic-associated diarrhoea Incidence and duration	Poisson regression.	Negative binomial regression (if Poisson over-dispersed).
All- cause diarrhoea (incidence and cumulative days)	Poisson regression.	Negative binomial regression (if Poisson over-dispersed)
Mean duration of diarrhoea episodes	A two-level Cox PH (frailty) model with infections nested within participants.	
Secondary – Health Utility		
Health utility (EQ5D)	Two linear regressions (EQ5D at 3/12 months separately) controlling for baseline EQ5D.	Transformations for normality.
Well-being (ICECAP-O)	Two linear regressions (ICECAP-O at 3/12 months separately) controlling for baseline ICECAP-O.	Transformations for normality.
Hospital stays	Logistic regression.	Poisson/negative binomial regression of counts (mean rate of hospital stays).
Death	Logistic regression.	Cox PH model for time from randomisation to death.
Secondary - Antimicrobial		

Resistance		
Presence of Gram-negative isolates in stools	Two logistic regression (stool sample finding at 3/12 months separately) controlling for baseline stool sample finding.	
Vancomycin resistant enterococci in stools	Two logistic regressions (stool sample finding at 3/12 months separately) controlling for baseline stool sample finding.	
Secondary - Mechanistic		
Immune parameters -Immune cell phenotypes -TLR ligand stimulated cytokines/chemokines -Plasma cytokines/chemokines -Monocyte and neutrophil phagocytosis -Flu vaccine response	Linear regression.	Transformation for normality.
Clostridium difficile in stools	Two logistic regressions (stool sample finding at 3/12 months separately) controlling for baseline stool sample finding.	
Presence of oral candidiasis	Two logistic regressions (response at 3/12 months separately) controlling for baseline response.	
Amount of oral candidiasis present in saliva	Two ordinal regressions (response at 3/12 months separately) controlling for baseline response.	
L. rhamnosus GG in stools	Two linear regressions (stool sample finding at 3/12 months separately) controlling for baseline stool sample finding.	Transformations for normality.
Bifidobacterium animalis subsp. lactis (BB-12)	Two linear regressions (stool sample finding at 3/12 months separately) controlling for baseline stool sample finding.	Transformations for normality.
Full blood count	Linear regression	Transformations for normality.
Flu vaccine response - titer	Linear regression	Transformations for normality.
Flu vaccine response - seroconversion and seroprotection	Logistic regression	

\* All sensitivity analyses will include a consideration of adherence to study product and the impact of missing data / deaths.

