#### **4.2 Rationale for current trial**

The 2010 Adult Social Care Statistics reported that there were 229,900 people in residential care in England, with numbers predicted to steadily increase. The 2011 census reported that there were 291,000 people over the age of 65 resident in the care home population in England and Wales (20). CHR are particularly prone to infections. The year-long observational study (n=274) identified 609 infections that led to an antibiotic prescription (incidence of 2.16 antibiotic prescriptions per resident year, 95% CI 1.90-2.46). The most common indications were RTI (47% of prescriptions), urinary tract infections UTI (29%) and skin infections (18%) (2). CID in CHR led to suffering, loss of dignity, hospitalisation, GP visits and death. Health needs assessment of 240 CHR in South Tyneside PCT identified 167 hospital admissions accounting for 1595 bed days over a year (21). On average, at least 4 beds in the Acute Trust are used for CHR all year round costing around £400K. About 25% of admissions were due to infection costing £100K in one PCT, or an estimated £54M/year for the UK. CIDs in CHR increase GP and care home burden and costs, impacting on opportunities for other aspects of care. Antibiotic prescribing leads to HCAIs such as *C. difficile* and drives AMR. The greatest risk of being infected with a AMR compared to a sensitive bacteria is recent consumption of antibiotics, even after controlling for age, comorbidity and other risk factors (22). AMR infections are more serious, last longer and are more costly to manage (23). Probiotics are effective in preventing AAD (5, 19), but we have no adequate data on prevention of all-cause common infections and antibiotic prescribing in care home residents.

There is an urgent need to reduce AMR through infection prevention in care homes. Urinary tract infections (UTIs) are usually caused by auto-inoculation; that is infection from our own bowel organisms. Carriage of AMR bowel organisms increases the chances of an AMR UTI. AMR Gram-negative septicaemia and AMR UTI are on the increase in the community, especially among older people (24). Care homes are a reservoir for AMR that cycle between the community and hospitals (3, 25). There is a steady increase in the care home population, and evidence-based interventions are needed to improve their quality of life through reducing the incidence of CIDs and antibiotic use (26).

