## **17.2 Sample size**

### **Primary Outcome**

The original target for the PRINCESS trial was to randomise 330 participants from around 20 care homes in Wales and England. This would provide 90% power at the 5% level to demonstrate a 10% relative reduction in cumulative antibiotic administration days (CAAD) (assuming an average CAAD of 17.4 days and an absolute reduction in the probiotic arm to 15.6 days per resident-year). We consider that a 10% reduction is feasible and would be clinically important.

This sample size accounted for 30% of participants being lost to follow-up due to withdrawal or death during the study.

An interim assessment of primary outcome ascertainment revealed that the mean percentage of days for which there are valid antibiotic administration data (i.e. either no antibiotics administered, or the number of days antibiotics have been administered in a given week) is 77.4%, or 283 days out of a possible 365 on average. This percentage varies depending on the length of time participants have been in the study. However, it remains high for participants who have been in the study for over six-months, and does not take into account other data sources that might be used (e.g. hospital discharge summaries, medication administration records, etc.). This is likely to therefore reflect an underestimate of the availability of primary outcome data, but nevertheless is a more accurate reflection of the likely level of follow-up when compared to our original assumption.

Given slower than anticipated recruitment, and this new information regarding the trade-off between the number of participants required and average length of follow-up, we will aim to randomise between 258 and 270 participants. Assuming a mean number of days for which primary outcome data will be available (i.e. accounting for follow-up time and missing data) of approximately 250 days, this will provide at least 82% power to detect a 10% relative reduction in CAAD.

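### Protocol 18.1 and the 18.2 table name different primary analyses for over-dispersed antibiotic days; if the table is followed with model-based standard errors, the false-positive rate for CAAD is about 49% or more

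*Protocol*

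**What the plan says.** Protocol section 18.1 describes the primary analysis as a "between-group comparison of the mean cumulative antibiotic administration days (CAAD) using Poisson regression", by intention to treat and controlling for care home. The same paragraph adds: "Negative binomial regression will be used in the presence of over-dispersed count data". Read plainly, negative binomial then takes the place of Poisson.

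The table in section 18.2 has separate columns for the main analysis and for sensitivity analyses. In the CAAD row the main analysis is Poisson regression, without qualification. The sensitivity column holds "Negative binomial regression (if Poisson over-dispersed", so under the table negative binomial stays secondary even after over-dispersion has been found. The same two entries appear for CAAD by infection type, incidence of infection, site of infection, cumulative infection days, antibiotic-associated diarrhoea and all-cause diarrhoea. The protocol mentions no robust or scaled standard error.

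The figures that bear on dispersion are the 17.4 antibiotic days per year (sections 3.3 and 17.2) and, in section 4.2, an "incidence of 2.16 antibiotic prescriptions per resident year, 95% CI 1.90-2.46", based on 609 prescriptions in 274 residents. Sections 3.3 and 4.2 cite the same earlier care-home study.

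**The concern.** Poisson regression with model-based standard errors assumes that the variance equals the mean. Days on antibiotics do not behave that way, because they arrive in courses: one prescription adds several days at once. The variance is then a multiple of the mean, and the standard error is too small by the square root of that multiple. This can be foreseen from the protocol's own numbers.

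Two things are at stake. Two analysts who each follow one section could report different primary p-values and intervals from the same data, and a nominally significant plain Poisson result could be presented as the planned main analysis. And if the table is the version followed, that p-value and interval would not be valid.

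**Working it through.** **1. The plan's own sample size.** Section 17.2 aims for 90% power at the 5% level with 330 randomised and 30% loss, "assuming an average CAAD of 17.4 days and an absolute reduction in the probiotic arm to 15.6 days per resident-year". Sidedness is not stated; two-sided is assumed. With variance equal to the mean:

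n per arm = (1.960 + 1.282)² × (λ1 + λ2) / (λ1 − λ2)²

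- λ2 = 15.66 (exactly 10% lower): 10.507 × 33.06 / 1.74² = 114.7, so 115 per arm, 230 in total, and 230 / 0.7 = 329. This reproduces the stated 330.
- λ2 = 15.6 (as printed): 107.02, so 216 in total, and 216 / 0.7 = 309.
- Revised design, means scaled by 250/365, λ2 = 15.66: power is 81.2% with 258 participants and 82.9% with 270. The plan states at least 82%.

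The planning therefore used a variance-to-mean ratio (φ) of 1.

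**2. φ from whole courses.** Days per prescription = 17.4 / 2.16 = 8.06. If the number of courses is Poisson with mean μ and each lasts L days, the mean of the total is μL and its variance μL², so φ = L = 8.06. Unequal course lengths raise φ further.

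**3. φ allowing for variation between residents.** From the interval 1.90 to 2.46, SE(log rate) = ln(2.46/1.90) / 3.92 = 0.066. A pure Poisson count of 609 gives 1/√609 = 0.041. The variance ratio, from unrounded values, is 2.64.

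- Full year: φ = 2.64 × 8.06 = 21.3.
- At 250 days: the implied between-resident (gamma) variance is (2.64 − 1) / 2.16 = 0.76. Expected courses are 2.16 × 250/365 = 1.48. The ratio for courses is 1 + 0.76 × 1.48 = 2.12, so φ = 2.12 × 8.06 = 17.1.

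**4. Type I error of plain Poisson.** With true variance φ × mean, error = 2 × [1 − Φ(1.96/√φ)].

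| φ | Interval too narrow by √φ | Type I error |
|---|---|---|
| 2 | 1.41 | 17% |
| 4 | 2.00 | 33% |
| 8.06 | 2.84 | 49% |
| 17.1 | 4.14 | 64% |
| 21.3 | 4.62 | 67% |

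**5. Simulation check.** Settings: 258 participants, 250 days, 20 homes as fixed effects in the Poisson models, no treatment effect, 1,000 trials per scenario.

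| Scenario | Mean φ | Plain Poisson | Poisson, robust variance |
|---|---|---|---|
| Poisson arrivals, 8-day courses | 8.0 | 47% | 6.1% |
| Between-resident variance 0.76 | 16.9 | 66% | 5.8% |
| Between-resident variance 1.0 | 19.2 | 68% | 6.3% |

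Negative binomial, fitted without home effects to 300 trials per scenario, rejected in 0.3%, 0.7% and 1.0%. A separate run with home effects gave 51% for plain Poisson, 6% for robust Poisson and 2% for negative binomial. No between-home variation was built into the 1,000-trial scenarios.

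**The case against.** The best defence is that this is a labelling slip. The prose of 18.1 defines the primary analysis, and its pointer to the table stands in the sentence on secondary outcomes, so for CAAD the prose should govern. The table is abbreviated: its Poisson rows omit the care-home adjustment that 18.1 requires. Its sensitivity column also holds other fallbacks for failed assumptions, such as transformations of skewed outcomes. Under 18.1, the over-dispersion predicted here would itself trigger negative binomial. The statistical analysis plan, not at hand, may settle the matter.

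Much of this stands. A reader might infer that the protocol commits the trial to a false-positive rate near 50%. It does not: that rate needs the table to override 18.1 and model-based standard errors to be used. Nor is a pre-stated switch on over-dispersion an error in itself.

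It does not remove the contradiction. The columns are labelled as main and sensitivity, and the negative binomial entry applies precisely when Poisson is over-dispersed. For the secondary counts, 18.1 itself sends the reader to the table. An analysis plan would have to overrule one of two protocol statements.

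A reader might also infer that the rows with an arm-by-infection-type interaction ignore the correlation of several records within a resident. The table names a model and an interaction and says nothing on data layout or variance estimation. That silence does not support the inference, and such detail is commonly left to the analysis plan.

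**Conclusion.** The contradiction between 18.1 and 18.2 is established from the text. Its possible consequence for the primary outcome is large: about 49% type I error at φ of about 8, and about 64% to 67% at φ of 17 to 21, if plain Poisson with model-based standard errors is taken as the main analysis.

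The protocol gives no dispersion value. The figure of 8 assumes that 17.4 days and 2.16 prescriptions describe the same residents and that days accrue in whole courses. The higher values also rely on the interval 1.90 to 2.46, part of which may be variation between homes that care-home adjustment would absorb. The 49% does not use that interval, and even φ = 2 gives 17%.

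These sizes apply to CAAD only. It would be tempting to carry them over to the other count rows, but the protocol gives no comparable figures for infection or diarrhoea days, and episode counts have no course multiplier. For those rows the finding is the contradiction alone. It would also be tempting to call negative binomial the exact cure. In these simulations it prevented false positives but was conservative, at about 2% or less where course arrivals were purely Poisson.

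**What to change.** Amend 18.1 and 18.2 so that both name the same main analysis for CAAD and the other Poisson count rows, valid under over-dispersion and fixed before unblinding. Preferred: Poisson regression with robust (sandwich) variance, adjusted for care home, which held type I error near 6% in simulation. Keep negative binomial as the sensitivity analysis, and remove plain model-based Poisson as the main analysis.

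The cost is wording, analysis code and wider intervals: for CAAD about 2.8 times as wide as plain Poisson intervals at φ of 8. The change makes the inference valid but does not restore power. With 258 participants, 250 days and φ of 8.06, power for a 10% reduction is about 17%, because the sample size was built on φ of 1.
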